10.0 DATA REPORTING / REGULATORY CONSIDERATIONS

Adverse event lists, guidelines, and instructions for AE reporting can be found in Section 7.0 (Adverse Events: List and Reporting Requirements).

10.1 Data Reporting

The Overture Database will be utilized, as required by the Case Comprehensive Cancer Center, to provide data collection for both accrual entry and trial data management. Overture is a Clinical Trials Management System housed on secure servers maintained at Case Western Reserve University. Access to data through Overture is restricted by user accounts and assigned roles. Once logged into the Overture system with a user ID and password, Overture defines roles for each user which limits access to appropriate data. User information and password can be obtained by contacting the Overture Administrator at [contact].

Overture is designed with the capability for study setup, activation, tracking, reporting, data monitoring and review, and eligibility verification. This study will utilize electronic Case Report Form completion in the Overture database. A calendar of events and required forms are available in Overture

10.2 Regulatory Considerations

The study will be conducted in compliance with ICH guidelines and with all applicable federal (including 21 CFR parts 56 & 50), state or local laws.

10.2.1 Written Informed consent

Provision of written informed consent must be obtained prior to any study-related procedures. The Principal Investigator will ensure that the subject is given full and adequate oral and written information about the nature, purpose, possible risks and benefits of the study as well as the subject's financial responsibility. Subjects must also be notified that they are free to discontinue from the study at any time. The subject should be given the opportunity to ask questions and be allowed time to consider the information provided.

The original, signed written Informed Consent Form must be kept with the Research Chart in conformance with the institution's standard operating procedures. A copy of the signed written Informed Consent Form must be given to the subject. Additionally, documentation of the consenting process should be located in the research chart.

10.2.2 Subject Data Protection

In accordance with the Health Information Portability and Accountability Act (HIPAA), a subject must sign an authorization to release medical information to the sponsor and/or allow the sponsor, a regulatory authority, or Institutional Review Board access to subject's medical information that includes all hospital records relevant to the study, including subjects' medical history.

10.2.3 Retention of records

The Principal Investigator of The Case Comprehensive Cancer Center supervises the retention of all documentation of adverse events, records of study drug receipt and dispensation, and all IRB correspondence for as long as needed to comply with local, national and international regulations. No records will be destroyed until the Principal Investigator confirms destruction is permitted.

10.2.4 Audits and inspections

Authorized representatives of the sponsor, a regulatory authority, an Independent Ethics Committee (IEC) or an Institutional Review Board (IRB) may visit the site to perform audits or inspections, including source data verification. The purpose of an audit or inspection is to systematically and independently examine all study-related activities and documents to determine whether these activities were conducted, and data were recorded, analysed, and accurately reported according to the protocol, Good Clinical Practice (GCP), guidelines of the International Conference on Harmonization (ICH), and any applicable regulatory requirements. For multi-center studies, participating sites must inform the sponsor-investigator of pending audits.

11.0 STATISTICAL CONSIDERATIONS

This study is designed as a feasibility study, with the goal of accruing 5 patients over the course of one year from trial opening. The primary objective is to determine the feasibility of TFRT planning and delivery in a modern clinical workflow. Feasibility is defined as a patient starting radiotherapy within 15 days of simulation. The TFRT technique will be deemed feasible if 3/5 patients meet the above criteria.

Descriptive statistics will be applied. Secondary endpoints include estimates of (1) acute grade 3-5 toxicity as per CTCAE version 4, (2) estimates of patient-reported outcomes during and after TFRT delivery using EORTC QLQ-H&N35, EORTC QLQ-C30, and Xerostomia Questionnaire (XO) and (3) compliance with plan delivery.

The patient-reported outcomes (PROs) from the above questionnaires will be collected at week 1 (baseline), week 4, and week 7 of treatment, as well as 2 weeks, 4 weeks, and 3 months post completion of treatment radiation. Descriptive associations between PROs and CTCAE toxicity criteria will be reported.

REFERENCES

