4/10/19	Title Page	Study coordinator name and contact info changed.
4/10/19	7.1.3	Clarification on AE's that are to be reported in the database.
5/8/20	Title Page, 7.3.1	PI changed from [name] to [name], additional study staff updated

STUDY SCHEMA

X

PROTOCOL SUMMARY

Protocol Number/Title	CASE4318 Feasibility Study of Temporally Feathered Radiation Therapy (TFRT) for Head and Neck Squamous Cell Carcinoma: Means of Toxicity Reduction
Study Phase	Feasibility
Brief Background/Rationale	
Intensity-modulated radiation therapy (IMRT) has allowed for optimization of three-dimensional spatial radiation dose distributions permitting target coverage while reducing normal tissue toxicity. However, acute and late radiation-induced normal tissue toxicity is a major contributor to patients' quality of life and often a dose-limiting factor in the definitive treatment of cancer with radiation therapy. We propose the next logical step in the evolution of IMRT incorporates canonical radiobiological principles, optimizing the temporal dimension through which radiation therapy is delivered to further reduce radiation-induced toxicity by increased time for normal tissue recovery. This new technique of radiation planning and delivery is termed Temporally Feathered Radiation Therapy (TFRT). TFRT has been previously modeled in silico and has demonstrated potential to reduce normal tissue toxicity. Given that TFRT is dependent on normal tissue recovery, a dynamic normal tissue complication probability (NTCP) model is used to ascertain the potential benefits of TFRT as compared to conventional IMRT planning. In this study, we will examine the feasibility of generating and delivering TFRT plans in the modern clinical workflow. Importantly, the radiation dose to the target volume is not altered and therefore this technique of radiation planning only examines techniques to reduce toxicity. All radiation prescription doses used in this study are determined as per current standards of care.

Primary Objective	
Primary Endpoints
 
Feasibility of TFRT planning and delivery defined as patient starting radiation within 15 days of CT simulation.

Secondary Objective(s)	
Secondary Endpoints
 
 (1) Estimate acute grade 3-5 toxicity (within 90 days after RT) (2) Patient-reported outcomes of toxicity during and after TFRT. (3) Compliance with plan delivery

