2.0 Objectives

2.1 Primary Objective

To determine feasibility of TFRT planning and delivery for head and neck squamous cell carcinoma defined as patient starting radiation within 15 days of simulation.

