6.6 Treatment Planning, Assessment and Delivery

6.6.1 **Planning Temporally Feathered Radiation Therapy:** The treating physician will designate up to 5 organs at risk (OARs) to be feathered based on proximity to target, prior to treatment planning. As shown in Figure 1, 5 *subplans* (designated as plan A, plan B, plan C, plan D, and plan E) will be generated, with each deprioritizing one of the 5 OARs. The **plans are considered to be isocurative** based on meeting standard guidelines for PTV coverage as described in 6.2.2.

- For each of these subplans, a single OAR is deprioritized such that it receives a higher dose (d_H) while the remaining 4 OARs receive a lower dose (d_L) than the standard fractional dose (d_S) delivered in a conventional IMRT plan.
- The daily dose delivered to the PTV is still 2 Gy.
- The OARs that may be feathered include, but are not limited to, the following: oral cavity, each submandibular gland, each parotid gland, OARpharynx, supraglottis, larynx, and esophagus.
- A standard IMRT plan must also be generated. If the patient cannot be started on the TFRT plan within 15 days of simulation, the standard IMRT plan should be delivered instead.
- **Note:** If the patient's start date for radiation therapy is delayed for medical reasons (eg dental extractions) not related to the timing of TFRT planning, TFRT planning can still be continued as planned. Delays in radiation start date must be designated whether directly attributable to TFRT planning.

Refer to appendix III on correct procedures for resumption of treatment schedule after a missed fraction.

6.6.2 Assessing Temporally Feathered Radiation Therapy: The treatment plan documents signed by the physician will be stored in Mosaiq. The treatment plan documents must include the treatment fields, the isodose lines, and DVH composite plan (labeled as COMPOSITE). Appendix III lists all of the components necessary in the approved treatment plan document.

Each subplan must be assessed individually in addition to the composite plan.

1. *Assessment of the composite plan:* The composite plan and DVH must be generated from the cumulative dose delivered by each of the 5 temporally feathered subplans. The composite plan must meet the compliance criteria as in 6.8.

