2. *Assessment of each subplan:* d_H is defined as a measure of dose distributed over a deprioritized organ. The max point dose for d_H must comply with: 0.03 cc of the deprioritized organ cannot exceed $>10\%$ of the prescription dose. The dose delivered to each PTV must meet the compliance criteria as in 6.8.

6.6.3 Delivery of Temporally Feathered Radiation Therapy: The patient should start radiation treatment within 15 days of CT simulation. If the patient is unable to be started on TFRT treatment plan within 15 days of the date of CT simulation, the patient must start radiation therapy using the standard IMRT plan previously created (and not TFRT plan) so as not to delay treatment schedule.

The treatment plan can be started on any day of the week, as long as at least 2 consecutive fractions are delivered before the weekend.

Specific IMRT QA should be performed for each subplan to ensure plan integrity.

Two therapists must be present for the delivery of TFRT. The therapists should continue with standard time out procedures with an additional verification that the correct subplan is selected for treatment according to the day of the week as in Appendix II. It is strongly encouraged that the attending physician or physicist to be present at the first 5 fractions of TFRT delivery.

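### The feasibility endpoint does not require the on-time start to be on TFRT, so a patient switched to standard IMRT and started by day 15 counts as a TFRT success

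*Combined protocol and SAP*

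**What the plan says.** The primary endpoint is defined in three places, each time by the start of radiation in general:

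- Protocol Summary: "Feasibility of TFRT planning and delivery defined as patient starting radiation within 15 days of CT simulation".
- Section 2.1: "To determine feasibility of TFRT planning and delivery for head and neck squamous cell carcinoma defined as patient starting radiation within 15 days of simulation".
- Section 11.0, which also gives the decision rule: "Feasibility is defined as a patient starting radiotherapy within 15 days of simulation. The TFRT technique will be deemed feasible if 3/5 patients" meet that criterion.

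Section 6.6.1 makes a standard IMRT plan mandatory for every patient and adds: "If the patient cannot be started on the TFRT plan within 15 days of simulation, the standard IMRT plan should be delivered instead". Section 6.6.3 repeats the instruction and gives its purpose: "the patient must start radiation therapy using the standard IMRT plan previously created (and not TFRT plan) so as not to delay treatment schedule".

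No section says how a patient who takes this fallback is scored. Section 6.6.1 asks for delays to be labelled as attributable or not to TFRT planning, but does not link the label to the endpoint. Section 3.3 allows replacement of subjects who leave the study for reasons unrelated to the treatment course, and does not mention patients switched to IMRT. Compliance with plan delivery is a secondary endpoint and plays no part in the 3/5 rule.

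**The concern.** The fallback exists to keep radiation on schedule, and radiation on schedule is what the endpoint scores. When TFRT planning runs late and the clinic starts IMRT by day 15, the technique under test has failed for that patient, yet the written criterion is met. The rule then cannot separate the feasibility of TFRT from the clinic's ability to start ordinary IMRT on time.

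The margin is thin. With a threshold of three out of five, moving one patient from success to failure turns 3/5 into 2/5 and reverses the conclusion. How a switched patient is scored should therefore be fixed before data are seen.

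A second, smaller gap is that the objective covers both planning and delivery, while the criterion is met at the first of 35 fractions. Nothing in it concerns delivery after that.

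**Working it through.** **Side-by-side reading.** Section 6.6.3 first says the patient should start radiation within 15 days. It then treats being unable to start on the TFRT plan as a separate event, whose consequence is to start radiation therapy on the IMRT plan. In the protocol's own usage, an IMRT start is a start of radiation therapy. More specific wording (started on the TFRT plan) appears in 6.6.1 but not in any of the three endpoint definitions.

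**Inputs from the documents.** n = 5 in a single arm (3.1, 3.2); threshold 3 of 5, read as at least 3 (11.0). No alpha, power or reference rate is stated, so the plan has no figure to reproduce.

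**Assumed inputs.** Neither rate is in the documents, so both are shown over a range:

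- p = probability that a patient starts TFRT within 15 days.
- f = probability that a patient for whom TFRT is not ready starts standard IMRT on or before day 15.

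Patients are taken as independent with common p and f.

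**Formulas.** Per-patient success probability:

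- TFRT starts only: π = p
- As written: π = p + (1 − p)f

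Probability of declaring feasibility: P(X ≥ 3) = 10π³(1 − π)² + 5π⁴(1 − π) + π⁵.

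**Worked case, p = 0.2.**

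- TFRT only, π = 0.2: 10(0.008)(0.64) + 5(0.0016)(0.8) + 0.00032 = 0.0512 + 0.0064 + 0.00032 = 0.058.
- As written with f = 0.5, π = 0.2 + 0.8 × 0.5 = 0.6: 10(0.216)(0.16) + 5(0.1296)(0.4) + 0.07776 = 0.3456 + 0.2592 + 0.07776 = 0.683.

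**Range.** The f = 0 column is also the result when only TFRT starts count.

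| p | f = 0 | f = 0.25 | f = 0.5 | f = 0.75 | f = 0.9 | f = 1 |
|---|---|---|---|---|---|---|
| 0 | 0 | 0.104 | 0.500 | 0.896 | 0.991 | 1 |
| 0.2 | 0.058 | 0.317 | 0.683 | 0.942 | 0.995 | 1 |
| 0.4 | 0.317 | 0.593 | 0.837 | 0.973 | 0.998 | 1 |
| 0.6 | 0.683 | 0.837 | 0.942 | 0.991 | 0.999 | 1 |

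**Limiting case, with no assumed rates.** If no patient starts TFRT and all five start IMRT by day 15, the criterion reads 5/5 and TFRT is declared feasible.

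**The case against.** The strongest reply is that the protocol, read as a whole, means a TFRT start. Section 6.1 ties the same 15-day window to protocol treatment and then says patients will receive TFRT. The Protocol Summary and 2.1 label the endpoint as feasibility of TFRT planning and delivery. The delay-attribution note in 6.6.1 makes most sense if TFRT timing is what counts. No sentence says that an IMRT start is a TFRT success. This is fair evidence of intent, but none of it is in the criterion or the 3/5 rule, and it is a reason to write the intent down.

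The second reply is that the fallback may come too late to matter. No date is set for the decision to switch. If the switch is made only after day 15 has passed, the patient fails on either reading, f is 0 and the problem disappears. This stands as a limit on size. It does not remove the problem, because 6.6.3 also says radiation should start within 15 days and gives avoidance of delay as the reason for switching.

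Third, switches would be visible. Appendix II has the plan sequence confirmed in Mosaiq at each treatment, and compliance with plan delivery is reported. That makes an unnoticed false claim unlikely and partly answers the point about delivery after the first fraction. It does not change what the stated rule would conclude.

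**Conclusion.** The concern holds. As written, the rule can declare TFRT feasible on the strength of IMRT starts, so a positive primary result could not be read as evidence of TFRT feasibility without looking behind it. This is a fault in the stated decision rule, and it should be corrected.

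The existence of the fault rests on the text alone. Its size rests on the assumed p and f. It is nil when every fallback start falls after day 15, and it is largest when TFRT is seldom ready and the clinic is prompt with IMRT. At p = 0.2, the chance of declaring feasibility rises from 5.8% to between 31.7% (f = 0.25) and 99.5% (f = 0.9). It matters least when TFRT is nearly always ready.

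**What to change.** Use the same definition in the Protocol Summary, 2.1 and 11.0, for example: *A patient meets the feasibility criterion if the first fraction is delivered with an approved TFRT subplan within 15 days of CT simulation. A patient started on the standard IMRT plan because TFRT was not ready is a failure, stays in the denominator of five and is not replaced under 3.3.*

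Add one line on how to score a patient whose start is delayed for medical reasons unrelated to TFRT planning. The plan already leaves this open. The note in 6.6.1 lets TFRT planning continue for such a patient, while the fallback in 6.6.3 states no exception, so those two passages also need to be reconciled. The scoring choice should be fixed in advance, since one patient can decide the result.

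For delivery, either limit the success claim to on-time planning and start, or report beside it the number of patients treated on TFRT subplans throughout.

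The cost is wording in three places plus the added line. The clinical fallback itself need not change for this repair. No new data are needed, because the treatment record already shows which plan was delivered. The one drawback is that the observed success count may be lower.

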6.2 Dose Specifications

6.2.1 Dose Fractionation

Patients must be eligible to receive 70 Gy in 35 fractions to the primary target (PTV_7000) and to receive 56 Gy in 35 fractions to the elective volume (PTV_5600). The doses are prescribed at the edge of the PTV. Treatment will be delivered once daily from Monday to Friday over 7 weeks. Missed treatments can be compensated for by treating on the Saturday or Sunday of that week, or adding to the end of treatment.

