7.3 Reporting Procedures for Serious Adverse Events

For the purposes of safety reporting, all adverse events will be reported that occur from the day of registration through 90 days after the completion of the prescribed course of therapy. Adverse events, both serious and non-serious, and deaths that occur during this period will be recorded in the source documents. All SAEs should be monitored until they are resolved or are clearly determined to be due to a subject's stable or chronic condition or intercurrent illness(es). Related AEs will be followed until resolution to baseline or grade 1 or stabilization.

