9.0 STUDY PARAMETERS AND CALENDAR

9.1 Study Parameters

9.1.1 Screening Evaluation

Evaluations including that needed to establish diagnosis, will be used to determine the eligibility of each subject for study inclusion. All evaluations must be completed < 40 days prior to administration of protocol therapy.

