9.1.2 Treatment Period

Patients will be evaluated in consultation, at which time information will be gathered regarding trial eligibility. Subsequently, patients will undergo CT simulation, initiation of radiation delivery, and weekly on-treatment visits. Follow-up visits will occur 2 weeks, 4 weeks, and 3 months post completion of treatment. At the indicated visits below, toxicity will be assessed by way of CTCAE criteria and patient-reported quality of life questionnaires.

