9.2 Calendar

At the scheduled visits below the patients will undergo evaluation of toxicity with physician-assigned grade as per CTCAE V4 as well as patient reported outcome measures using EORTC QLQ-C30, EORTC QLQ-HN35 and Xerostomia Questionnaire (XQ) as demonstrated in Appendix IV.

A visit window of +- 4 days is allowed for the visits while the patient is undergoing treatment. A visit window of +- 7 days is allowed for the visits 2 and 4 weeks after completing treatment. A visit window of +- 28 days is allowed for the 3 month post-treatment.

Study Days	Wk 1 of RT (+- 4 days)	Wk 4 of RT (+- 4 days)	Wk 7 of RT (+- 4 days)	2 Wks post- RT (+- 7 days)	4 wks post RT (+- 7 days)	3 mos post RT (+- 28 days)
REQUIRED ASSESSMENTS						
Weight	X	X	X	X	X	X
Vitals (blood pressure, pulse, respiratory rate, and temperature)	X	X	X	X	X	X
Physical Examination	X	X	X	X	X	X
Adverse Event Assessment	X	X	X	X	X	X
PRO Assessment	X	X	X	X	X	X

Karnofsky PS	X	X	X	X	X	X
--------------	---	---	---	---	---	---

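### The week 1 questionnaire is called baseline, but the protocol text neither requires it before the first fraction nor fixes its day

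*Combined protocol and SAP*

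**What the plan says.** Section 11.0 states that the PRO questionnaires (QLQ-H&N35, QLQ-C30 and Xerostomia Questionnaire) "will be collected at week 1 (baseline), week 4, and week 7 of treatment", with further forms 2 weeks, 4 weeks and 3 months after radiotherapy. One time point is thus called both baseline and on-treatment.

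Section 9.1.2 ties PROs to the calendar visits. The first column of the 9.2 calendar is week 1 of radiotherapy; there is no earlier one. Section 9.2 adds: "A visit window of +- 4 days is allowed for the visits while the patient is undergoing treatment". It does not name the day from which the four days are counted.

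On the pre-treatment period, 9.1.1 says "All evaluations must be completed < 40 days prior to administration of protocol therapy", but it refers to diagnosis and eligibility and names no PRO. Section 9.1.2 then gives the sequence after consultation: "patients will undergo CT simulation, initiation of radiation delivery, and weekly on-treatment visits".

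The start day varies between patients. Section 6.2.1 says "Treatment will be delivered once daily from Monday to Friday over 7 weeks", and 6.6.3 says the plan "can be started on any day of the week, as long as at least 2 consecutive fractions are delivered before the weekend", which in effect allows Monday to Thursday starts.

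The analysis in 11.0 is descriptive. It defines no change score, and there is no comparator arm.

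**The concern.** A baseline is normally the patient's state before the intervention. Here the value given that name belongs to the treatment period, and nothing in the protocol text keeps it ahead of the first fraction. Two patients can both comply, one with a form completed before any radiation and the other with a form completed after several fractions.

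What is at stake is how each patient's PRO course is read. The H&N35 asks about mouth and throat pain, swallowing, teeth and hoarseness. Patients with oropharyngeal, laryngeal, hypopharyngeal or nasopharyngeal tumours may have these problems before treatment, and only a pre-treatment value separates existing symptoms from those that arise on treatment. Concurrent chemotherapy is allowed (4.1.2) and its timing is not given. If it starts in week 1, the QLQ-C30 items on appetite, nausea and vomiting could already have moved by the time of the form.

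Section 1.2.2 reports no earlier clinical data on TFRT, and 1.3 looks ahead to later studies powered for toxicity, so the PRO course is part of what this trial hands on. With five patients, differences in the timing of the reference value will not average out.

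**Working it through.** The plan gives no figure for exposure at baseline, so there is none to reproduce. What can be counted is how many fractions a compliant form may follow.

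**Inputs.** 35 fractions, Monday to Friday, over 7 weeks (6.2.1); 2 Gy per day to the PTV (6.6.1); Monday to Thursday starts (6.6.3); window ±4 days (9.2). Consistency check: 7 × 5 = 35 fractions and 35 × 2 = 70 Gy, as in 6.2.1.

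**Assumptions.** Day 1 is the day of the first fraction. No fraction is missed or given at a weekend. The anchor day is not in the documents, so each anchor below is assumed. The lowest count has the form completed before that day's fraction; the highest has it completed after.

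**Fractions delivered before a compliant week 1 form**

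| Reading of week 1 | Days allowed | Mon start | Tue | Wed | Thu |
|---|---|---|---|---|---|
| Any of days 1–7, window not used | 1 to 7 | 0–5 | 0–5 | 0–5 | 0–5 |
| Day 1 ± 4 days | 4 days before RT to day 5 | 0–5 | 0–4 | 0–3 | 0–3 |
| Day 3 ± 4 days | 2 days before RT to day 7 | 0–5 | 0–5 | 0–5 | 0–5 |

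On all three readings the range starts at zero and ends at no more than 5 fractions: 5 / 35 = 14.3% of the course, or 5 × 2 = 10 Gy to the PTV. That is target dose, not dose to the glands and mucosa that the questionnaires reflect. For example, if the parotid goal in 6.7 is met (mean below 26 Gy over the course), one cycle of five subplans delivers under 5/35 × 26 = 3.7 Gy mean.

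**Recall period.** The H&N35, the Xerostomia Questionnaire and the QLQ-C30 items under the past-week heading ask about the preceding week; QLQ-C30 items 1–5 do not. For a form on day d, the pre-treatment days among the previous seven number max(0, 8 − d):

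| Form on day | 1 | 2 | 3 | 4 | 5 | 6 | 7 |
|---|---|---|---|---|---|---|---|
| Pre-treatment days | 7 | 6 | 5 | 4 | 3 | 2 | 1 |

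If the form day itself counts as one of the seven, the formula is max(0, 7 − d). Under either count, a form on days 2 to 6 mixes pre-treatment and on-treatment days.

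These are counts of exposure. The documents give nothing from which to estimate the resulting shift in PRO scores.

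**The case against.** The strongest reply is that no planned analysis uses the baseline. Secondary endpoint 2 is PROs during and after TFRT, summarised descriptively in five patients, and the only further analysis named is a descriptive association with CTCAE grade. Section 1.1 also says acute radiation toxicity appears mid-way or late in the course, so a form a few fractions in may differ little from a pre-treatment one. This stands, and it is why the point is minor. It does not remove the point: the plan itself calls this value baseline, so readers will use it as the reference.

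A second reply is that sites will naturally give the form on day 1 before delivery, or that the electronic calendar settles the day. Such a form would comply and would be a true baseline. Section 10.1 does say "A calendar of events and required forms are available in Overture", and that calendar is not among the documents. The finding is therefore about the protocol text, which does not require this timing.

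Three stronger readings are tempting, and the documents do not support them:

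- A reader might add the four days to the end of week 1, reach day 11 and count up to 9 fractions. No section supplies such an anchor. It would accept a form from treatment week 2 as the week 1 form, and it needs full use of the window and a Monday or Tuesday start.
- A reader might infer that the baseline is always contaminated by treatment. On the three readings tabulated, a pre-treatment form is permitted.
- A reader might extend the gap to adverse events, since 7.3 says "Related AEs will be followed until resolution to baseline or grade 1 or stabilization" while 9.2 has no pre-treatment column. But 7.3 also accepts grade 1 or stabilization, 7.1.3 requires events after consent to be fully recorded in the medical record, and 9.1.1 and 9.1.2 provide for evaluation before treatment.

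**Conclusion.** The point holds as a minor one. On the protocol text, the questionnaire labelled baseline need not be pre-treatment and need not fall at a common point across the five patients. A compliant form can follow anywhere from 0 to about 5 fractions within week 1, and more only under other assumed anchors. The count rests on the assumed anchors and on an uninterrupted weekday schedule.

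The consequence is confined to reading each patient's PRO course against that first value. The 3/5 feasibility rule, PRO levels at later visits and PRO-CTCAE associations at later visits do not depend on it. The direction and size of any shift in scores cannot be determined from the documents. The case for acting is that the change costs almost nothing, while a missing pre-treatment value cannot be obtained afterwards.

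**What to change.** - In 9.2 and 11.0, define the PRO baseline as the three questionnaires completed after consent and before the first fraction, with no plus window. Day 1 before delivery would meet this.
- Either move the week 1 form to that point, which needs no extra forms, or keep week 1 as a separately labelled on-treatment time point, which adds at most five sets of questionnaires (one per patient).
- State the anchor day for the week 1 (if kept), week 4 and week 7 windows.
- For any patient already treated, report the date of the form and the fractions delivered by then, and label forms completed after the first fraction as on-treatment.

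The cost is amendment wording in two sections. Sample size, the feasibility rule and the descriptive analysis stay as they are.
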